6.5 Primary and Secondary Outcome Measures

The primary outcome measure:

Speech intelligibility. This refers to how easy it is to understand the child's speech. This is measured with:

- The Intelligibility in Context Scale (ICS; McLeod et al., 2012). ICS is an assessment to rate the intelligibility of children's speech in their daily environments.

- Word Intelligibility by Picture Identification (WIPI; Ross & Lerman, 1979). WIPI assesses the intelligibility of the child's speech in single words.

The secondary outcome measures:

1: Communicative participation - This is measured with:

- Focus On Communication Under Six assessment (FOCUS; Thomas-Stonell, et al., 2004). FOCUS is an assessment for parents to rate their perception of their child's communicative participation and confidence in everyday situations. Although FOCUS is designed for children aged 3-6 years, it is used in this study because there are no other assessment tools that measure communicative participation with older children. Previous studies in CP have reported the use of FOCUS with older children (Pennington, et. al., 2013).

- Speech Participation and Activity Assessment of Children (SPAAC; McLeod, 2004). SPAAC is a child-directed rating tool of participation levels for children with speech disorders.

2: Parent/ Carer and child satisfaction with participant's communicative participation. These are measured with:

-The Canadian Occupation Performance Measure (COPM; Law, et al., 2005). COPM is a goal-setting tool and an outcome measure. Participants are directed through a semi-structured interview to set intervention goals and to rate performance and satisfaction. This is done before and after the intervention.

Page 13 of 21 The effectiveness of Rapid Syllable Transition Treatment in improving communication in children with cerebral palsy: A randomized controlled study

3: Speech accuracy. This is measured with:

- Percentage of phonemes correct in word level. The percentage of phonemes correct (PPC) expresses the percentage of consonant sounds that are articulated correctly. It is considered a robust means of assessing articulation accuracy (Shriberg et al., 1997) and will allow comparison with previous ReST research.

4: Sentence complexity. - This is measured with:

- Mean length of utterance (MLU) in speech. Changes in the child's mean length of utterance, as measured by calculating the average number of morphemes in a child's utterances (Miller & Chapman, 1981).

- Mean Length of Utterance with an augmentative and alternative communication system (AAC). This is only applicable to children who have a high technology AAC system. MLU is measured from the sentences produced on the high technology AAC system.

6.6 Interventions

6.6.1 Rapid Syllable Transition Treatment (ReST; McCabe et al., 2017)

ReST involves the child saying multisyllabic pseudowords to improve the ability to transition rapidly and fluently from one sound/syllable to the next, and control of the melody in the form of relative emphasis, or stress, placed on each syllable within a word (McCabe et al., 2017). Based on the baseline assessment, four vowels and four consonants are selected and used to form pseudowords, for example, consonants b, p, k, and m are combined with vowels to create pseudo-words bamaka, makaba, mikabu and bamipa. The practise phase includes 100 attempts at producing the pseudowords. The level and type of feedback are controlled. If the child is unable to complete all 100 pseudowords within the session, the remaining unfinished pseudowords are practised in additional sessions after the 12th session until a total of 1200 productions is achieved.

6.6.2 Who provides the intervention?

The intervention is provided by The University of Sydney speech pathology students under the supervision of the speech pathologists in the research team. The students will be trained by the study coordinator in the treatment and data collection before the commencement of the intervention block. Supervision is provided throughout the intervention block and in accordance with Speech Pathology Australia and The University of Sydney speech pathology supervision guidelines.

6.6.3 Usual Care Group

Children randomised to the usual care control group will continue to receive their usual care therapy. Families will fill in a weekly online questionnaire that includes questions about i) the family's satisfaction with the child's speech, ii) use of the child's high technology AAC if the child has one, and iii) content and the dose of usual care therapy. Once the Treatment phase 1 Follow up assessment T3 has been completed, this group will begin ReST therapy. The families in the Usual first- group are asked to fill in this questionnaire weekly and emailed to the study coordinator, [name] while they are waiting to commence treatment.

Page 14 of 21 The effectiveness of Rapid Syllable Transition Treatment in improving communication in children with cerebral palsy: A randomized controlled study

The families will email the questionnaire to the study coordinator. If the families neglect to answer the questions, the study coordinator will contact the family and remind the family to email the questionnaire. If the family is unable to email the answers, the questionnaire will be conducted over the phone with the study coordinator or the speech pathology students.

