6.2 Schedule of Events/ Treatment Phases

Table 1: Flowchart of the schedule of events

- 1. Rolling Recruitment: Please see section 6.4.1
- 2. Eligibility Screening: Participants will participate a screening assessment via teleconferencing. This will take 10 15 minutes.
- 3. **Baseline Assessment, T1**: All eligible participants will attend an initial assessment in person at the University speech pathology clinic or at the family's home. If this is not possible, the assessment will be conducted on teleconference.
- 4. The Consent form will be signed.
- 5. **Randomisation**: The children who are eligible to participate will be randomised to ReST first- group or usual care- group.
- 6. Treatment phase 1:
 - a. **ReST first- group:** Children in the treatment group will receive ReST therapy three times a week for six weeks, totalling 18 sessions.
 - b. Usual care- group: Children in the usual care group will continue their usual care therapy and complete T2 and T3 assessments. See Table 1, The Flowchart of the schedule of events. The content and dosage of usual care will be recorded. If the participant has a speech generating device, the frequency of use and device satisfaction will also be recorded.
- 7. **Treatment phase 1 Post intervention assessment, T2**: Within one week after the final ReST session.
- 8. **Treatment phase 1 Follow up assessment, T3:** Three weeks after the final ReST session.
- 9. Treatment phase 2:
 - a. **ReST first- group:** The children will complete T4 and T5 assessments.
 - b. **Usual care- group:** Children in the usual care group will commence ReST after T3 assessments are completed. See Table 1, The Flowchart of the schedule of events.
- 10. **Treatment phase 2 Post intervention assessment, T4**: Within one week after the final ReST session.
- 11. **Treatment phase 2 Follow up assessment, T5**: Three weeks after the final ReST session.

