9. DATA MANAGEMENT

9.1 Data collection and storage

Research data, including video recordings and assessment results are collected in electronic form. Identification codes replace names in all files.

All assessment and treatment sessions are videoed, which will then be uploaded by the treating student therapist to The University of Sydney approved Dropbox immediately after the session.

Paper copies of assessment forms are scanned and collected in electronic form.

Paper copies of intelligibility ratings are scanned and collected in electronic form.

The paper forms are shredded immediately after scanning.

The weekly online questions for the usual care group are collected weekly through REDCap survey and saved electronically.

Consent forms, contact details, and identifying codes will be held in a password protected encrypted file in the RDS.

Once the data is no longer being actively used it will be deleted from Dropbox and only retained in the RDS.

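### Only usual-care-first families rate their satisfaction with the child's speech every week up to T3, so the two arms reach T2 and T3 with different rating histories on a construct close to the parent-rated secondary outcomes

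*Protocol*

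**What the plan says.** Section 6.6.3 describes the weekly form: "Families will fill in a weekly online questionnaire that includes questions about i) the family's satisfaction with the child's speech". Its other two topics are use of a high-technology AAC device and the content and dose of usual care.

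The same section says who completes it and for how long: "The families in the Usual first- group are asked to fill in this questionnaire weekly", and they do so "while they are waiting to commence treatment". ReST begins for this arm only once T3 is done, so the form covers the whole run-up to both T2 and T3. Families who do not respond are reminded, and the form can be completed by phone with the study coordinator or the speech pathology students.

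Section 9.1 agrees on the recipients: "The weekly online questions for the usual care group are collected weekly through REDCap survey and saved electronically".

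Section 6.2 gives a different list for the usual-care arm: "The content and dosage of usual care will be recorded", and "If the participant has a speech generating device, the frequency of use and device satisfaction will also be recorded". Satisfaction with speech is not in that list. For the ReST-first arm, section 6.2 gives the treatment schedule ("Children in the treatment group will receive ReST therapy three times a week for six weeks, totalling 18 sessions") and then the T4 and T5 assessments in phase 2. It mentions no weekly family rating in either phase.

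In section 6.5, communicative participation is measured partly by a parent report: "FOCUS is an assessment for parents to rate their perception of their child's communicative participation and confidence in everyday situations". Parent or carer satisfaction with communicative participation is a separate secondary outcome, measured with COPM. Section 6.4.5 states that participants are not blinded; only the clinicians who score the assessments are.

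**The concern.** The usual-care arm is asked week after week to judge how satisfied the family is with the child's speech, during a period when that family knows it is waiting for the study treatment. The ReST-first arm is not asked. At T2 and T3, parents in both arms report on related constructs, and the planned group-by-time ANOVA in section 6.14 compares them.

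Repeated rating can change how a person uses a scale, through practice, recalibration or a change in expectation. If that happens in one arm only, the ANOVA cannot separate it from a treatment effect. Randomisation gives no protection, because the difference is created after allocation by one arm's procedures. Blinding of the scoring clinicians gives none either, because the parent makes the rating.

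What is at stake is the interpretation of the parent-reported part of hypothesis 2 (communicative participation) and of the satisfaction outcome. In return the form yields a weekly satisfaction series that can be set against nothing in the other arm.

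**Working it through.** The protocol states no figure for this point, so there is nothing to reproduce. The check compares sections and counts ratings.

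**1. Is the rating confined to one arm?** Section 6.6.3 assigns the form to the usual-care-first families, and section 9.1 repeats this. Section 6.2 gives the ReST-first arm no weekly form in phase 1, when it receives ReST, or in phase 2, when it only attends T4 and T5. The form therefore goes with the sequence, not with the usual-care condition, and the cross-over does not even it out. That it is confined to one arm rests on sections 6.6.3 and 9.1 and on silence elsewhere; no sentence explicitly excludes ReST-first families.

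**2. How many ratings?** Inputs from section 6.2: 6 weeks of ReST, T2 within 1 week of the final session, T3 at 3 weeks after it. Assumptions: one form per week, and usual-care visits on the same calendar as the ReST arm.

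| Assessment | Usual-care-first, per family | ReST-first, per family |
|---|---|---|
| Before T2 | 6 to 6 + 1 = 7 | 0 |
| Before T3 | 6 + 3 = 9 | 0 |

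With 10 families per arm (section 6.3), that is 9 × 10 = 90 one-arm ratings before T3. Section 6.6.1 allows additional sessions when productions are unfinished. If these lengthened the ReST calendar, the count would rise.

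**3. Which outcomes are close to the item?**

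| Measure | Who reports | Close to the weekly item? |
|---|---|---|
| FOCUS (secondary) | Parent | Yes: parent perception of communication, though not satisfaction as such |
| COPM (secondary) | Parent or carer and child | Yes: includes satisfaction, but with communicative participation and individual goals |
| ICS (primary) | Not stated | Only if families complete it, which would be an assumption |
| SPAAC (secondary) | Child-directed | No parent rating stated |
| WIPI, phonemes correct, MLU | Not parent ratings | No |

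**4. Do sections 6.2 and 6.6.3 contradict each other?** Section 6.6.3 names speech satisfaction and not device satisfaction; section 6.2 does the reverse. But 6.6.3 says the form includes its three topics, and 6.2 says certain items will also be recorded. Neither list claims to be complete. They are unaligned, not contradictory.

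**5. Can the effect be sized?** Not from the protocol. As an illustration only, take a shift of d standard deviations in one arm, 10 per arm, and a two-sided t test at 5% with 18 degrees of freedom. The noncentrality is d × √(10/2) and the critical value is 2.101.

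| Assumed shift d | Noncentrality | Rejection rate with no treatment effect |
|---|---|---|
| 0.1 | 0.224 | 5.5% |
| 0.2 | 0.447 | 7.1% |
| 0.3 | 0.671 | 9.7% |

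The shifts are assumed, and this is not the repeated measures ANOVA that section 6.14 plans. The table shows only that a small shift would do little and a larger one would not be trivial. It does not estimate this trial's error rate.

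**The case against.** The strongest reply is that this is a monitoring form and that harm from it is conjecture. The protocol holds no evidence that a weekly question moves later FOCUS or COPM scores. Practice and recalibration could move ratings either way, and added attention to speech could raise usual-care scores and so work against ReST. Parents are unblinded in any case, and ReST families attend three sessions a week, so expectations already differ between arms; the increment from one weekly item may be small. COPM is described as done before and after the intervention, so a COPM comparison between arms at both T2 and T3 is not established. The series also has some use, since it describes change within families during usual care.

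All of this stands as a limit on the claim. It does not remove the asymmetry, which is on the face of the text, serves no comparison and can be removed.

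A reader might infer four stronger things that the protocol does not support:

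- **That any shift would be counted in favour of ReST.** The direction is unknown.
- **That the false-positive rate rises to somewhere between 5.5% and about 10%.** Those figures depend on invented shifts and on a test other than the planned one.
- **That the primary outcome is biased.** WIPI is not a parent rating, and section 6.5 does not say who completes the ICS.
- **That sections 6.2 and 6.6.3 contradict each other.** Both lists are open-ended.

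**Conclusion.** The point holds as a minor, avoidable design weakness. As written, usual-care-first families rate speech satisfaction weekly, about 6 to 7 times before T2 and about 9 before T3, while ReST-first families do so no times. The counts assume that usual-care visits follow the ReST calendar; the zero rests on the absence of any such form for that arm.

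The arms therefore differ in rating history, as well as in treatment, when unblinded parents report on FOCUS and, at the occasions where it is given, COPM. Whether this shifts scores, by how much and in which direction cannot be determined from the protocol. The reach shown is limited to these secondary outcomes. The point concerns one-arm rating of a construct near the outcomes; recording the content and dose of usual care is sound and should stay.

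**What to change.** Choose one of two edits to section 6.6.3 and the matching survey form:

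- **Drop the item.** Remove satisfaction with speech from the weekly usual-care form, leaving content and dose of care and AAC use. The cost is a within-family descriptive series during usual care.
- **Ask it equally.** Take the item off the weekly form and put it to both groups with identical wording and timing, for example at each of T1 to T5. The cost is one extra short item for ReST-first families and some overlap with COPM.

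In either case, align the item lists in sections 6.2 and 6.6.3 so that both describe the same form. Do not settle the difference by adding device satisfaction as a new weekly item in one arm, since that would recreate a one-arm satisfaction rating. Beyond these costs, the change needs a small form edit and a line or two of protocol text, submitted as a modification under section 6.10.

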6.7 Participant Withdrawal

Participants will be informed in the Participant Information Statement about their right to withdraw at any time. If the participant wishes to withdraw, they are asked to inform the study coordinator or another of the investigators. At this point, parents will be asked if they wish the researchers to retain or destroy already collected data. If the participant agrees, then their data will be retained and analysed using intention to treat analysis. If the participant does not agree, then their data will be destroyed. Parents who decide to withdraw from the research will be asked for their reasons and these will be recorded and reported if they are provided and if consent is provided.

6.7.1 Non-Compliance

A participant's non-compliance with the treatment protocol will be addressed with the family by either the student speech pathologist or the student's supervisor. If the family is unable or unwilling to follow the treatment protocol, they will be advised to discontinue the program. The family will then be asked if they wish the already collected data to be retained or destroyed. If the participant agrees to retention, then their data is recorded. If the participant does not agree, then their data is destroyed. The reasons for non-compliance will be asked and if provided, they will be recorded and reported in the results if consent is provided.

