6.7.2 Handling of withdrawals and losses to follow-up

Intention to Treat (ITT) will be used to statistically analyse the results if there is loss to follow up, or if there are any deviations from the original assigned groups.

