6.7.3 Participant Replacement following withdrawal

Replacements will not be sought for participants who withdraw from the study, as attrition has been accounted for in our sample size calculations.

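### Section 6.7.1 ties non-adherence to leaving the study and to a retain-or-destroy question, which undermines the promised intention-to-treat analysis, one-sidedly in phase 1

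*Protocol*

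**What the plan says.** Section 6.7.1 (Non-Compliance) stands under 6.7 (Participant Withdrawal). It says: "If the family is unable or unwilling to follow the treatment protocol, they will be advised to discontinue the program". It continues: "The family will then be asked if they wish the already collected data to be retained or destroyed". The two answers lead to "If the participant agrees to retention, then their data is recorded" and "If the participant does not agree, then their data is destroyed". The section does not mention T2 to T5 assessments for a child who stops.

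For families who withdraw of their own accord, section 6.7 is more explicit: "If the participant agrees, then their data will be retained and analysed using intention to treat analysis". If they refuse, "If the participant does not agree, then their data will be destroyed".

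Section 6.7.2 says: "Intention to Treat (ITT) will be used to statistically analyse the results if there is loss to follow up", and extends this to departures from the assigned groups. Section 6.14 repeats the ITT commitment for any attrition.

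**The concern.** Adherence is known only after randomisation and may be related to outcome. ITT protects the comparison only if children who do not adhere still have outcomes and are counted in the group to which they were allocated. Section 6.7.1 works against this in three ways:

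- The study team itself advises the family to stop. No request to withdraw is needed.
- The study team then raises destruction of the data.
- No later assessment is provided for. A child who stops before T2 would have no post-baseline outcome even if the family lets the data be kept.

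At stake is the first hypothesis in section 4, that ReST improves intelligibility more than usual care. If children for whom the sessions were too hard or unhelpful drop out of the ReST-first group, the phase 1 comparison moves towards ReST adherers against all controls, and the trial says less about how well ReST is tolerated.

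**Working it through.** **1. The sections side by side**

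| Situation | Trigger | Kept data | Later assessments |
|---|---|---|---|
| Withdrawal (6.7) | the family's wish | retained and analysed by ITT | not stated |
| Non-compliance (6.7.1) | the team's advice | *recorded*; analysis not mentioned | not stated |
| Loss to follow-up, group deviation (6.7.2), attrition (6.14) | any | ITT promised | not stated |

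The ITT promise needs outcomes that 6.7.1 may cause to be destroyed or not collected.

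**2. Which group is exposed, and when**

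- Phase 1 (T1 to T3): under 6.2 the ReST-first group has 18 ReST sessions over six weeks. Under 6.6.3 the other group carries on with its existing therapy, and a missed weekly questionnaire leads to a reminder or a telephone call, not to advice to stop. Only the ReST-first group has a ReST protocol to breach.
- Phase 2 (after T3): the usual-care-first group starts ReST, so 6.7.1 applies to it too. If such a family chooses destruction, the child's phase 1 control data go as well.

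**3. The plan's own sample size**

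Inputs from 6.3: d = 1.376 and 10 per group. Alpha 0.05 and power 0.80 are stated there for a neighbouring calculation and are assumed to carry over; a two-sided test is assumed. The noncentral t solution is 9.36 per group, rounded up to 10. The plan's figure is reproduced.

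**4. Power when k ReST-first children are lost**

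The noncentrality is d × √(n₁n₂/(n₁+n₂)), with n₁+n₂−2 degrees of freedom:

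- 10 v 10: 1.376 × √(100/20) = 3.077, power 0.829
- 9 v 10: 1.376 × √(90/19) = 2.995, power 0.806
- 8 v 10: 1.376 × √(80/18) = 2.901, power 0.777
- 7 v 10: 1.376 × √(70/17) = 2.792, power 0.742

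**5. Inflation of the effect**

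Assume that adherent children gain e, that k of 10 are non-adherent and gain a fraction f of e, and that all k are lost.

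- ITT effect: e × (10 − k + fk)/10
- Estimate from those left: e
- Ratio: 10/(10 − k + fk)

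With f = 0 the ratio is 10/9 = 1.11, 10/8 = 1.25 and 10/7 = 1.43 for k = 1, 2 and 3. With k = 2 and f = 0.5 it is 10/9 = 1.11. With f = 1, or if nobody is lost, it is 1.

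**6. If ReST has no effect**

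Assumptions: 40,000 simulated trials per setting, adherence correlated 0.3 to 0.5 with outcome, the k least adherent of 10 ReST children lost, two-sided t-test at 0.05.

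| k | Spurious benefit (SD) | False significant result favouring ReST (nominal 2.5%) |
|---|---|---|
| 1 | 0.05 to 0.09 | 3.2% to 3.8% |
| 2 | 0.10 to 0.16 | 4.0% to 5.2% |
| 3 | 0.14 to 0.23 | 4.4% to 6.7% |

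**The case against.** Much can be said for the plan, and several stronger readings that a reader might infer do not hold.

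- *Non-compliant children are removed from the study.* The text speaks of discontinuing the program, and 6.7 uses different words for leaving the research. That 6.7.1 means leaving the study is an inference. It is the natural one, given the heading it stands under, the reference to data collected so far and the silence on follow-up, but it is not stated.
- *ITT is defeated.* Destruction depends on the family's answer, and retention is the other half of the same question. Where data are kept, ITT is weakened at most. Whether data that are only *recorded* enter the analysis could be settled in an analysis plan. What no analysis plan can do is restore outcomes that were destroyed or never collected.
- *Only the ReST arm loses children.* That holds for phase 1 alone. Over the whole cross-over both groups are exposed.
- *The effect will be overstated by 25%.* This is one assumed case, two children lost with no benefit in either. The protocol gives neither a non-compliance rate nor a rate of choosing destruction. Some families will be unable to continue for practical reasons unrelated to response, and such losses need not favour ReST.

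A family's wish to have data deleted on withdrawal is a legitimate consent matter. Nor is the rule that "Replacements will not be sought for participants who withdraw from the study" an error; it only means that losses are not made good.

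**Conclusion.** The concern holds in a limited form. Followed as written, 6.7.1 links a post-randomisation event, non-adherence, to probable loss of outcomes, and so conflicts with the ITT commitments in 6.7.2 and 6.14. In phase 1 the loss would fall on the ReST-first group and would probably favour ReST.

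The size cannot be predicted from the protocol. Each lost child is a tenth of an arm. For one to three children lost, the inflation is 1.11 to 1.43 times if they gain nothing, less if they gain something, and none if all are retained and assessed. Power falls from 0.83 to between 0.81 and 0.74 at the plan's own d. The power loss is modest; the possible bias is the main reason to act. The change should be made, and before enrolment, because destroyed data cannot be recovered.

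**What to change.** Leave the decision to stop therapy as it stands. In 6.7.1:

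- state that stopping ReST is not withdrawal from the study;
- state that these children are invited to all remaining scheduled assessments;
- state that their data are analysed in the allocated group, in line with 6.7 and 6.7.2;
- remove the retain-or-destroy question where non-compliance is the only trigger.

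Leave the choice in 6.7 unchanged for families who withdraw from the research, and report any destroyed data by arm.

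The cost is wording in the protocol and information sheet, submission to both ethics committees before implementation and a registry entry (6.9 and 6.10), and some assessments of children no longer treated, which are already in the schedule.
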